5 STUDY ENROLLMENT AND WITHDRAWAL

5.1 Inclusion Criteria

In order to be eligible to participate in this study, a practitioner must meet all of the following criteria:

- Is enrolled in the National Dental PBRN as a limited or full participation network member;
- Is a practitioner or a dental care professional and has completed an Enrollment Questionnaire;
- Is licensed in the U.S. to treat patients, treats patients in the U.S. on a recurring basis, and maintains an active practice address at which he or she can be contacted;

5.2 Strategies for Recruitment

5.2.1 Practitioner Recruitment

Eligible practitioners for the survey will be identified based on the criteria noted from their responses on the PBRN Enrollment Questionnaire. All eligible practitioners will first receive an alert letter informing them of the survey, followed by a study invitation email inviting them to participate in the study. The alert letter and invitation will include a link to the electronic version of the survey. Based on previous regional PBRN questionnaire studies, we anticipate a response rate of approximately 80%. Calls will be made as needed with the Regional Coordinators (RCs) to review contact information for eligible practitioners, and assist in response encouragement. For the interviews, we will use purposive sampling, recruiting eligible participants from each region. Study team members will work with RCs to invite eligible participants to engage in the interviews.

Practitioners will be reimbursed \$50 for participation in the survey and \$50 for participation in an interview. This is a single survey questionnaire study with interviews; retention strategies are not applicable.

5.3 Subject Withdrawal

Practitioners may choose not to participate in the study and/or withdraw voluntarily from the study for any reason at any time without penalty. Practitioners who withdraw from the study will not be replaced.

5.4 Premature Termination or Suspension of Study

This study may be suspended or prematurely terminated if there is sufficient reasonable cause. Written notification, documenting the reason for study suspension or termination, will be provided by the suspending or terminating party. If the study is prematurely terminated or suspended, the study principal investigator (SPI) will promptly inform the IRB and will provide the reason(s) for suspension or termination.

Circumstances that may warrant termination include, but are not limited to:

- Determination of unexpected, significant, or unacceptable risk to study participants.
- Insufficient adherence to protocol requirements.
- Data that are not sufficiently complete and/or evaluable.
- Determination of futility.

6 STUDY SCHEDULE

6.1 **Practitioner Survey**

Eligible practitioners will be identified based on their responses to the Enrollment Questionnaire and will be invited to complete an online questionnaire over a period of approximately 3-4 months during the first year of study implementation. Agreement to enter the survey will indicate tacit consent per Georgia Tech IRB regulations (a standard waiver of consent for web-based surveys).

The invitation mail/email schedule will be detailed in the Data Management Plan.

6.2 **Practitioner Interviews**

Study team members will work with regional coordinators to identify and invite up to 60 eligible participants to engage in the telephone interviews.

Each interview will last approximately 45-60 minutes. Telephone interviews will occur during year 3 of study implementation.

7 STUDY PROCEDURES/EVALUATIONS

7.1 Survey Development and Administration

Practitioner Survey Development

This survey was developed by our study team, a group with expertise in questionnaire development and implementation, and was internally tested by the clinicians who are part of the team. Following the development of the survey, the instrument was reviewed by Program Officials at the NIDCR. The survey has been programmed in the Survey Management System (SMS) and uploaded and is ready for field pretesting.

Cognitive Interviewing

Cognitive testing of the survey instrument was completed in early December 2015. Team members Drs. [name], [name], and [name] conducted six 60 minute interviews with three general dentists and three hygienists. The Executive Committee review of the instrument was also very helpful, and resulted in specific changes to the instrument. This process provided an opportunity to review the survey in detail with dentists and dental hygienists, and to also test its timing. These practitioners were invited to the complete the online survey via a unique ID and password. Once completed, they were provided with a printout of the blank survey codebook to facilitate conversation with the team member who interviewed them about their experience. Interviewers reviewed their responses to a completed survey, and probed to assess possible respondent problems in understanding questions, recalling necessary information, and/or reporting accurately. Based on team discussion, a small set of questions were also flagged for specific probes during these interviews. We asked participating practitioners how relevant they thought the items in the draft survey were to addressing information related to ANP and other disruptive products, and whether any issues relevant to ANP were not addressed in the survey. From the Executive Committee review and the detailed cognitive interviews, minor wording changes to add clarity and understandability were made. Completion time for the survey was 20-34 minutes.

Website and Survey Testing

The survey was programmed in Sawtooth Software (licensed by Georgia Tech) and has been uploaded to an online site for testing. The study team performed extensive internal testing of the survey website, including internet browser compatibility. Study team members (e.g., SPI, National Network Director (NND), Regional Directors, Statistician and Regional Coordinators (RC)) will be given the opportunity to externally test the website prior to administration with study participants.

Survey Pilot- testing

The online version of the survey will be administered to approximately 100 practitioners to assess the reliability of the survey. Based on cognitive interviewing, the survey is expected to take 20- 30 minutes to complete. The field test will provide a more complete understanding of survey timing prior to the full implementation.

Survey Content

Some information will be collected from the National Dental PBRN Enrollment Questionnaire (e.g., demographics and practice characteristics) and linked to participants' responses to the study survey. Topical areas addressed in the survey are detailed in Section 3.

Survey Administration

Eligible participants, i.e., dentists and hygienists, will be identified from their responses to the network's enrollment questionnaire. Skip logic may also be incorporated in the survey in order to provide an additional screening mechanism.

A waiver of documentation of signed informed consent will be required for participants to enter the survey. Consistent with regulations outlined by the Georgia Tech (GT) IRB, information about the study as well as their rights as participants, will be provided to all eligible practitioners in the postal invitation mailing as well as in the electronic survey prior to the start of the survey questions.

The survey will be administered by the Georgia Tech team. The survey process will follow Dillman (2000) survey methods, and will include an alert letter sent via US mail as well as an email notice, and periodic reminder emails. All eligible participants will receive a study invitation alert letter one week in advance of the email notification and invitation to the survey. Participants will receive a unique user ID and password that will be needed to enter the survey. Due to the complexity of the survey, as well as cost constraints, a paper survey will not be used as an alternative.

If no feedback is received or the participant does not complete the survey after multiple follow up attempts over a period of three to four months, it is assumed the practitioner has declined to participate in the study.

7.2 Interview Guide Development and Administration

Interview Guide Development

Decisions on this process for development and the content of the focus group interview guide will be reached at a later date, and will depend upon observed trends and findings from other study activities. *No interviews will be conducted until IRB approval for those data collection instruments is complete.*

Interview Administration

Informed consent procedures will be performed prior to participation in the interview. Consistent with regulations outlined by the Georgia Tech (GT) IRB, information about the study will be provided to all eligible practitioners in an email invitation to participate in the interview, as well as verbally from the interviewer prior to the start of the interview. Interviews will be conducted by study team members. Interviews will be audio-recorded and transcriptions will be completed for each interview. Data from the interview transcriptions will be coded and analyzed for thematic issues using NVivo software (text analysis software). Transcriptions will be conducted as

interviews are completed in order to manage work flow. Study team members ([name], [name], [name]) will do spot checks on the transcriptions to ensure quality and completeness.

Each interview will last approximately 45-60 minutes and will be conducted in an invited telephone conference call format to maintain confidentiality. The specific instrument for these interviews will be developed following the completion of the initial analysis of the study survey data.

8 ASSESSMENT OF SAFETY

8.1 Specification of Safety Parameters

Safety monitoring for this study will focus on unanticipated problems involving risks to participants.

8.1.1 Unanticipated Problems

The Office for Human Research Protections (OHRP) considers unanticipated problems involving risks to subjects or others to include, in general, any incident, experience, or outcome that meets **all** of the following criteria:

- Unexpected in terms of nature, severity, or frequency given (a) the research procedures that are described in the protocol-related documents, such as the IRB-approved research protocol and informed consent document; and (b) the characteristics of the subject population being studied;
- Related or possibly related to participation in the research (possibly related means there is a reasonable possibility that the incident, experience, or outcome may have been caused by the procedures involved in the research); and
- Suggests that the research places subjects or others at a greater risk of harm (including physical, psychological, economic, or social harm) than was previously known or recognized.

8.2 Reporting Procedures

Incidents or events that meet the OHRP criteria for unanticipated problems require the creation and completion of an unanticipated problem report form. OHRP recommends that investigators include the following information when reporting an adverse event, or any other incident, experience, or outcome as an unanticipated problem to the IRB:

- Appropriate identifying information for the research protocol, such as the title, investigator's name, and the IRB project number;
- A detailed description of the adverse event, incident, experience, or outcome;
- An explanation of the basis for determining that the adverse event, incident, experience, or outcome represents an unanticipated problem;
- A description of any changes to the protocol or other corrective actions that have been taken or are proposed in response to the unanticipated problem.

Per Georgia Tech guidelines, investigators are required to *report to the Institutional Review Board within ten days of its occurrence* any serious problem, serious adverse event, or other outcome that occurs more frequently or with greater severity than anticipated. Further, if any event(s) cause the suspension, whether temporary or permanent, of a research study involving human subjects, the IRB must be informed within ten days. Such reports to the IRB must describe the adverse events' relevance and significance to the study and whether there is a change in the risk of participation.

Any reported harm as a result of study participation will be reported to the Georgia Tech Office of Research Integrity. Guidelines on reporting violations or harm are as follows:

"Anyone with a concern about any aspect of research involving human subjects at Georgia Institute of Technology or who wants to report a violation of these Policies and Procedures may contact the Institutional Official/VPR, the IRB Chair, any IRB member, a Research Associate, or the Executive Director or Associate Director of Research Integrity Assurance. Concerns may also be emailed to [contact]. Reports made to the Office of Research Integrity Assurance will be delivered to the IRB Chair and the Institutional Official/VPR for further action."

To satisfy the requirement for prompt reporting, unanticipated problems will be reported to NIDCR within 2 weeks of the investigator becoming aware of the problem.

 All unanticipated problems should be reported to appropriate institutional officials (as required by an institution's written reporting procedures), the supporting agency head (or designee), and OHRP within one month of the IRB's receipt of the report of the problem from the investigator.

All unanticipated problems will be reported to NIDCR's centralized reporting system via Rho Product Safety:

- Product Safety Fax Line (US): [name]
- Product Safety Fax Line (International): [contact]
- Product Safety Email: [contact]

9 STUDY OVERSIGHT

The GPI and SPI will be responsible for study oversight, including monitoring safety, ensuring that the study is conducted according to the protocol and ensuring data integrity. The SPI will review the data for safety concerns and data trends at regular intervals, and will report to the IRB and NIDCR any unanticipated problem, protocol deviation, or any other significant event that arises during the conduct of the study, per the IRB's reporting time-frame requirements. To ensure data integrity, the SPI and study team will adhere to quality management processes (see Section 13).

10 CLINICAL SITE MONITORING

Clinical site monitoring will not occur for this study, however data monitoring will occur. The SPI is responsible for launching the survey, performing interviews, and collecting data received through the survey and interviews. Quality assurance (QA)/Quality Control (QC) activities associated with data collection and processing will be outlined in the data management plan (DMP). The SPI will ensure that the quality and integrity of study data and data collection are maintained.

11 STATISTICAL CONSIDERATIONS

11.1 Study Hypotheses

Due to the exploratory nature of the data gathered in this study, no formal hypothesis will be presented here.

11.2 Sample Size Considerations

A stratified sample of eligible PBRN members will be invited to participate in the survey. Detailed analysis of the composition of the PBRN membership list will be necessary to make the final sampling plan. Our probability sampling approach will be used with the goal of achieving a confidence level of 95% with a 3-5% margin of error. Our preliminary expectation is that approximately 500 individuals from each of the six regions will be selected for the survey sample. For regions with lower enrollment, the population in that region will be included in the survey. This number will provide sufficient flexibility to address sampling stratification needs. The final sampling plan will be completed once the PBRN enrollment questionnaire data and full contact list are available to the SPI.

We will use a cluster-based sampling approach to ensure comparability across PBRN regions, together with a stratified random sample of participants in order to ensure a representative sample that would be consistent with the characteristics of the population of practicing dentists and dental hygienists (Blair and Blair, 2014). As part of our research questions, and motivated by theoretical and empirical work on under-represented groups and organization theory, any sampling strategy would require at a minimum stratification by gender, age, race/ethnicity, dental specialization, practice type, PBRN region, and rural/urban status.

An important part of the analytical plan will also include an assessment of non-response bias based on PBRN composition. Depending upon the results of this analysis, additional follow-up with particular respondents may be required.

The study team will also consider a data weighting approach depending on the composition of the PBRN membership. If this is necessary, the sample weights for the survey will be developed and included in the final data set.

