4 STUDY DESIGN

This is a multi-methodological 39-month study involving an online survey, a series of interviews, multiple stages of bibliometric data collection, and web scraping for non-academic publications in key media sources and online dental discussion boards. The strength of this approach is that it blends self-reported behavioral and attitudinal data (survey and focus group data) with evidence of knowledge transfer data (publication and other print/media/discussion board) in order to provide a detailed analysis of dental knowledge needs, sources, available resources and networks, and knowledge pathways. Primary data collection will involve a survey of dental practitioners enrolled in the PBRN network (dentists and dental hygienists) and a series of interviews to be conducted via telephone.

Practitioner Survey:

To be eligible for the survey, practitioners must be enrolled in the National Dental PBRN and have completed an Enrollment Questionnaire. An estimated 4000 dentists and hygienists will be eligible to complete the survey (survey population frame), from which an estimated sample of roughly 415 practitioners per region (N=2500) will be drawn. The survey sample will be stratified by PBRN region, dentist/hygienist, as well as gender, race, specialty and practice type. The details of this sampling stratification will be refined once the PBRN enrollment survey data are provided to the study team by Westat. The survey will be implemented during the 1st year of study implementation, after the first round of bibliometric and web scraping. The duration of survey implementation is anticipated to be approximately five months. Development and administration of the questionnaire survey is detailed in Section 7.1.

Survey Pilot-Test Phase

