In addition to the descriptive analysis, we anticipate developing a series of multivariate regression models appropriate to the data set and questions. These models will be developed based on appropriate theoretical literature given the specific research question addressed, prior studies, and input from our study team. For example, dentist/hygienist, practice size, gender, and involvement in research and professional communities will be appropriate independent variables to test on overall interpersonal network size and resources. Among others, some key dependent variables of interest include: ANP screening behavior, ANP knowledge, clinical network resource levels, breadth of research engagement/cosmopolitanism (Bozeman and Corley, 2004) multiplexity and homophily of clinical information sources and resources (Lin et al., 2001), and others. Exploratory regression models will allow us to control for practice size, region, gender, and other variables on level of awareness of ANPs, ANP screening, as well as knowledge network resources. We foresee use of a variety of regression approaches in the analysis of the survey and membership data such as OLS, negative binomial, logit and probit modeling, as well as network analysis models, where appropriate.

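### Section 11.2 promises a sample representative of practicing dentists and hygienists, but the frame and non-response check cover only enrolled network members, so the design can neither ensure nor check this

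*Protocol*

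**What the plan says.** Protocol Section 11.2 plans a stratified random sample, combined with a cluster approach across regions, to "ensure a representative sample that would be consistent with the characteristics of the population of practicing dentists and dental hygienists". That population is not limited to the network.

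The operational text is limited to it:

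- **Eligibility.** Section 4 says "practitioners must be enrolled in the National Dental PBRN and have completed an Enrollment Questionnaire". The first criterion in Section 5.1 is "Is enrolled in the National Dental PBRN as a limited or full participation network member".
- **Frame.** Section 4 puts the survey population frame at an estimated 4000 eligible dentists and hygienists, all of them network members.
- **Sample.** Section 11.2 opens with "A stratified sample of eligible PBRN members will be invited to participate in the survey".
- **Non-response.** Section 11.2 plans an "assessment of non-response bias based on PBRN composition".
- **Weighting.** Section 11.2 says "The study team will also consider a data weighting approach depending on the composition of the PBRN membership", and weights are to be built only if that proves necessary.

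Section 11.2 aims for 95% confidence and a margin of error of 3-5%. Section 14.4 expects women and underrepresented minority groups to be oversampled. In Section 11.3.1 the profiles of information seekers are discussed in terms of the dental population as a whole. The same section says that "involvement in research and professional communities will be appropriate independent variables to test on overall interpersonal network size and resources".

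**The concern.** A probability sample supports inference to the list it was drawn from. Here the list is the network's enrolled members. Section 11.2 attributes to the sample a property with respect to a wider population, yet no planned step connects the two. No external workforce figures are named, members are not compared with non-members, and no limit on generalization is stated.

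At stake is how the survey results may be worded. If the sentence in Section 11.2 stands, percentages for information sources, ANP screening or network size could be reported as describing practicing dentists and hygienists, with a margin of error that covers sampling error among members and nothing else. The issue matters more than usual in this survey because enrollment in a research network is plausibly related to research involvement and professional engagement, which Section 11.3.1 uses as explanatory variables.

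**Working it through.** **1. What population does each element refer to?**

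| Element | Protocol section | Population |
|---|---|---|
| Representativeness statement | 11.2 | Practicing dentists and hygienists |
| Eligibility | 4, 5.1 | Enrolled network members |
| Frame (about 4000) | 4 | Enrolled network members |
| Sample | 11.2 | Eligible network members |
| Non-response check | 11.2 | Network composition |
| Weighting | 11.2 | Conditional; no benchmark stated |

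Only the first row extends beyond the network.

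**2. What does the stated margin measure?**

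Inputs: 95% confidence and 3-5% (Section 11.2); about 500 selected in each of six regions (11.2); 80% response (5.2.1); about 415 per region, N=2500, and a frame of 4000 (4). I take p = 0.5. Section 4 calls 415 and 2500 the sample drawn, while the Protocol Summary makes 2500 the goal for respondents. I treat them as respondents here; that discrepancy does not affect this point.

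Half-width = 1.96 × √[p(1−p)/n]

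- One region, n = 500 × 0.80 = 400: 1.96 × √(0.25/400) = 4.90 points
- One region, n = 415: 4.81 points
- All regions, n = 2500: 1.96 × √(0.25/2500) = 1.96 points

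With the finite population correction √[(N−n)/(N−1)], the overall figure for N = 4000 is 1.20 points. If the regions are equal in size (an assumption, N = 4000/6 ≈ 667), n = 400 gives 3.10 points.

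The 3-5% target is therefore reproduced at region level. The correction makes plain which population is meant: the margin goes to zero when all 4000 members respond. A complete census of the network would have no sampling error and would still contain no information on non-members. Section 11.2's provision to take everyone in low-enrollment regions has the same limitation.

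**3. What would a difference between members and non-members do?**

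Let W be the network's share of all practitioners, and M and U the true values in members and non-members. The all-practitioner value is W·M + (1−W)·U. A sample that estimates M without error therefore misses it by

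M − [W·M + (1−W)·U] = (1−W)(M−U).

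The sample size does not enter. The protocol gives neither W nor M−U. The following shows only how the formula behaves, on assumed values: W from 1% to 10%, n = 2500, standard error √(0.25/2500) = 1.00 point, no finite population correction.

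| Assumed M−U | Shift (1−W)(M−U) | Coverage of the all-practitioner value by a nominal 95% interval |
|---|---|---|
| 0 points | 0 | 95% |
| 2 points | 1.80 to 1.98 points | 56% to 49% |
| 5 points | 4.50 to 4.95 points | 0.6% to 0.1% |

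The shift may be nil or may exceed the sampling margin. Nothing in the plan would show which.

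**The case against.** The strongest reply is that Section 11.2 promises less than it seems to. It speaks of consistency with the characteristics of practicing clinicians and then lists stratifiers such as gender, age, specialization and rural/urban status. It also defers the final sampling plan until the membership list is available. A sample matched to the profession on those variables could be drawn from a member list if external targets were set. This shows that demographic resemblance is not out of reach. It does not justify the word *ensure*. No external targets are named, Section 14.4 plans oversampling, and weights are only to be considered. Matching on demographics would also not balance research engagement.

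Several further objections stand, and they rule out stronger readings:

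- **That the weights are tied to the network alone.** The weighting sentence states what the decision depends on, not what the weights would be calibrated to. It is compatible with weighting to an outside population.
- **That the non-response check is itself faulty.** Non-response is defined relative to the frame, so checking it against network composition is normal practice. It simply does not address coverage.
- **That members are self-selected volunteers.** The protocol says enrolled, with limited or full participation. Self-selection is an inference.
- **That the study's main results are affected.** The primary outcomes (Section 3.2.1) come from bibliometric and text-mining data. The survey serves the secondary outcome. Section 11.3.1 names research involvement as one example of a predictor beside profession, practice size and gender.

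The setting also softens the point. There are no formal hypotheses (11.1), Section 2.2 is cautious about generalizability, one stated use of the results is internal to the network (2.3.2), and the frame is disclosed openly.

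**Conclusion.** The mismatch is real and rests on the protocol's own text: the sample is said to represent practicing dentists and hygienists, while eligibility, frame and non-response check stop at the network and no external benchmark is named. The design can neither ensure nor check the stated property. The sampling and its margin of error support inference to eligible National Dental PBRN members, provided that unequal selection and non-response within the network are handled.

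A reader might go on to infer that the survey estimates are biased for the profession, or that associations with research engagement are distorted. The document does not support that. The link between enrollment and the survey variables is plausible, but no difference between members and non-members is given, and with no difference there is no bias. The size cannot be estimated, and the illustrative shifts above rest wholly on assumed values. The point deserves correction because it governs what the survey may conclude, but its reach is limited to secondary, exploratory results.

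**What to change.** In Section 11.2, replace the reference to the population of practicing dentists and hygienists with eligible National Dental PBRN members. State that the 3-5% margin of error applies to that population. Word the survey conclusions, including the information-seeker profiles in Section 11.3.1, in the same terms.

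Label any statement about all practicing dentists and hygienists as extrapolation. If the team wants to support one, it can add a sensitivity analysis that rakes the sample to external workforce margins such as age, gender, region and specialty, with the source named. This is optional. The protocol does not supply those margins, and raking would leave any selection on research engagement uncorrected, which should be said alongside the result.

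The cost is a change of wording and a narrower claim. The recommended change needs no new data collection and no change to the sample size.
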